### **9.3.2. Assessments during the Combination and the Monotherapy Phases**

A history, physical and neurological exam will be performed by a physician every 4 weeks before the avelumab infusion to determine if there is evidence of toxicity or tumor progression every 4 weeks for the first 12 weeks and then every 12 weeks or at the end of treatment and 30 days after.

A pre-infusion questionnaire and vital signs will be done by the nurse prior to each infusion (ieQ2weeks). If these suggest evidence of significant toxicity or tumor progression then the patient will be referred to the physician for evaluation.

Laboratory evaluations will be done prior to each infusion (i.e. Q2weeks) at the end of treatment and 30 days after to look for evidence of toxicity.

Non-study specified MRI or CT scan done for safety evaluations will be performed according to local standard practise usually Q3-4 months.

**Note:** An unscheduled disease assessment may be performed at the discretion of the investigator or at the request of the infusion nurse to ascertain if there is significant toxicity or clinical evidence of tumor progression

All AE's will be graded according to the NCI-CTC AE, version 5.0

### **9.3.3 Assessments during the Extended Safety Follow-up Phase:**

Patients will undergo a physical and neurological exam as well as hematological and blood chemistry and thyroid evaluations at day 30 post end of treatment and telephone follow-up calls monthly x2

Pathology samples will be obtained for repeat biomarker analysis if a second tumor surgery occurs

### **9.3.4. Assessments at end of study**

An end of treatment study visit will occur when:

- 1) Grade 3 or higher avelumab related toxicity occurs
- 2) Evidence as per the iRANO criteria of tumor progression occurs and patient does not wish to continue treatment
- 3) Patient wishes for any reason to discontinue treatment or withdraw from the study. Clinical evidence of neurological deterioration resulting in an ECOG score

of at least 3 or more, unexplained by other comorbidities, unchanged by an increase in corticosteroid dose and sustained for at least two weeks.

A history, physical and neurological exam will be performed by a physician. Laboratory test as per schedule will be drawn. If any of the latter have already been performed to confirm the AE or tumor progression on the basis clinical neurological deterioration, then they need not be repeated.

A study specified gadolinium enhanced MRI or CT scan will be performed within 2 weeks of the end of study visit for all patients after 52 weeks.

Patients however who discontinue the study treatment on the basis of avelumab treatment related AE's or clinical evidence of tumor progression a study specified MRI or CT scan will be done at the discretion of the investigator.

Patients who prematurely discontinue study treatment will be encouraged to continue into the Extended Safety Follow-up phase of the study

Patients who not only end treatment but also withdraw from the study, for any reason, will be encouraged to have telephone follow ups every month in order to obtain survival information with regards to OS. Pathology samples will be obtained for repeat biomarker analysis if a second tumor surgery occurs

**NOTE:** Since the actual duration of pseudoprogression and the time for immunotherapies to become effective in patients with GBM are still unknowns patients will be allowed at the investigator and patient discretion to continue on study treatment after confirmation of radiographic progression unless there is significant drug toxicity Grade 3 or higher AE's unrelated to avelumab such as those secondary to intercurrent illness or temozolomide therapy do not constitute for the purpose of this study a reason to withhold avelumab therapy or withdraw the patient from the study.

### **9.3.5. Disease assessment Evaluation**

Disease assessment evaluations will be based according to the immunotherapy Response Assessment for Neuro-Oncology (iRANO).

Study specified MRI's or CT scan will be done at the baseline, week 52 and every 52 weeks. These will be performed at a single MRI center using a predefined acquisition protocol (appendix 3). Change in the corticosteroid dose within the 2 week period preceding the week 52 MRI or CT scan will be discouraged.

All other MRI's or CT scan performed mainly for safety reasons will be done locally according to standard practise usually every 3 to 4 months. Copies of these MRI's or CT scan will be obtained for review by the investigator. These will also be used after the 6 month mark to ascertain if there is radiological evidence of progression according to the iRANO criteria (see page 29).

It is strongly encouraged that for a given patient the same physician will do the physical and neurological evaluations to confirm AE's or tumor progression during the entire study

**Neurological Examination:**

Evaluation of neurological function at each disease assessment will be based purely on the investigator's assessment of the patient's neurological state compared to the neurological function at the time of the last assessment visit. Neurological function must be recorded as Improved, Unchanged, or Worsened.

In the absence of progression based on radiological assessment, patients who clearly neurologically worsen compared to neurological evaluation at the last disease assessment, and whose corticosteroids use is unchanged or increased compared to the previous disease assessment, will be considered to have evidence of disease progression.

**NOTE:** Neurological deterioration independent from the disease being treated should not be considered in the context of the Disease Assessments.

**Corticosteroids use:** at the time of each disease assessment the corticosteroid intake will be compared to corticosteroid intake at the time of the last disease assessment. The changes and dose will be recorded as Increased, Unchanged or Decreased. Increases and decreases in corticosteroid intake should be clinically justified.

**NOTE:** Increases in corticosteroid dose for reasons other than for tumor disease control especially if done to control immune related AE's need to be recorded and taken into consideration when making this comparison.

The corticosteroid dose should be kept stable for 14 days prior to the 12 months MRI or CT scan in order to minimize interference of corticosteroids in the interpretation of response.

**Radiological assessment:** patients who have undergone gross total resection and show neither contrast-enhancing (index lesions) nor non-enhancing lesions (non- index lesions) on MRI or CT scan will be followed for recurrence (the appearance of one or more new lesions). If no signs of progression are observed on the MRI or CT scan, then these patients should have a radiological assessment recorded as "No Change". However, in case of unequivocal evidence of progressive disease (major deterioration in neurological function, and unchanged or increased corticosteroid dose) the Overall Disease Assessment will be "progressive disease". Progressive disease will not need a confirmatory scan.

For index lesions the Sum of the Product of the biperpendicular Diameters of the measurable enhancing lesions (SPD) will be recorded and used for comparison. An increase in the lesion SPD noted prior to month 6 will require confirmation 3 months later using the last MRI or CT scan as baseline comparison. The 12 months MRI or CT scan will be compared to baseline.

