## **Pseudo-progression in Glioblastoma**

Reactive changes and tumor necrosis early on (<3 months) post radiotherapy may lead to radiological tumor enlargement i.e. pseudoprogression. An incidence of >20% pseudo-progression has been reported early on post radiochemotherapy (12). Pseudoresponse has been reported with anti angiogenic therapies.

Pseudoprogression has also been reported in patients with solid tumors treated with immunotherapies such as CTLA-4 or avelumab. Early tumor enlargement or even new small distant lesions can be followed later by tumor regression. This could be explained by two possible explanations: immunotherapies require more time to implement tumor control and the initial pseudoprogression is actual progression which later responds; focal inflammatory responses can lead to tissue edema and swelling. The timeframe for immunotherapy induced pseudo-progression remains to be defined but can be present several months post initiation of treatment (37).

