**Progression of Disease (PD) based on radiographic parameters:**

Patients with stable clinical neurological status with stable dexamethasone dose of 12mg/day or less and evidence of radiological progression defined as a  $\geq 25\%$  increase in the sum of the biperpendicular diameters of enhancing disease; or substantial worsened T2/FLAIR; or new lesions on gadolinium enhanced MRI or CT scan done less than 6 months from baseline will require confirmation on a repeat imaging done 3 months later. The first MRI or CT scan showing progression will act as the new baseline and if progression is confirmed the date of progression will be backdated to the new baseline MRI or CT scan where the progression was first noted.

If the first radiological evidence of progression or new lesions occurs 6 months or more from baseline then no confirmatory imaging will be required.

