### **5.3. Exploratory**

The correlation between OS and PFS and the prevalence of PD-L1 expression on tumor cells and microglia/macrophages within the tumor, the histological immunoscore.

The correlation between OS and PFS and the baseline corticosteroid dose, the total cumulative corticosteroid dose over the whole study duration, the total cumulative dose of temozolomide since diagnosis, the baseline value and the change from baseline to week 52 visit and/or the end of study neurocognitive function as measured by the evoked potential P300 and the incidence and severity of irAE's.

The change between baseline biomarker results and those obtained from biomarkers in tissue samples from patients with second surgical resection i.e. treatment failures

The description of the time period in which radiological progression was seen in clinically stable patients whose imaging was subsequently followed by radiological stabilization or regression

The description of the time period in clinically stable patients before radiological evidence tumor regression occurred

The change in P300 evoked potential values and its correlation with clinical outcomes

**Safety monitoring:** There will be an internal DSMB which will make annual reviews.

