### **12.3.2. Secondary Endpoints**

Based on the results of Stupp *et al* (2005) (3), if avelumab had no effect then we would expect to see one-year overall survival and progression-free survival rates of 60% and 27%, respectively. We will conclude that we have preliminary evidence of benefit if either of our observed rates is significantly better based on a one-sided t-test at the 0.2 level of significance. With our projected sample of 30, this corresponds to concluding benefit if at least 21 patients survive to one-year or if at least 11 have survived without progression of disease.

Radiological tumor response will be graded according to the immunotherapy Response Assessment for Neuro-Oncology (iRANO)

**Progression of Disease (PD)** will be defined as a  $\geq 25\%$  increase on the 12 month MRI or CT scan in the sum of the product of the biperpendicular diameters of enhancing disease; or new lesions; or substantial worsened T2/FLAIR; or significant clinical neurological decline unexplained by a change in medication or concurrent comorbidities. The SPD is the sum of the products of biperpendicular diameters of the measurable enhancing lesions (max 5 lesions).

**Complete Response (CR)** will be defined as the disappearance on the month 12 MRI or CT scan of all enhancing disease, no new lesions, with stable or improved T2/FLAIR; no more than physiological steroids; clinically stable or improved

**Partial Response (PR)** will be defined as a  $\geq 50\%$  decrease on the month 12 MRI or CT scan in the sum of the product of the biperpendicular diameters of enhancing disease, no new lesions, stable or improved T2/FLAIR, stable ( $>2$  months) or decreased steroid dose, clinically stable or improved

**Stable Disease (SD)** will be defined at 12 months when a patient do not qualify for complete response, partial response, or progressive disease, stable or improved T2/FLAIR; stable ( $>2$  months) or decreased steroid dose, clinically stable or improved

**Overall survival (OS)** will be defined as the time from baseline to the date of death from any cause.

**Objective Response Rate (ORR)** will be defined the number of patients with either CR or PR divided by the total number of patients.

**Progression Free Survival (PFS)** will be defined as the time from baseline to documented PD or death from any cause.

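### The reference scan for size-based progression is not settled: baseline at month 12, a reset scan after early growth, no smallest-SPD rule, and a 25% threshold written in two different units

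*Protocol*

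**What the plan says.** **Month-12 reference.** Protocol 12.3.2 and SAP 1.3.2 define size-based progression as a rise of at least 25%, an "increase on the 12 month MRI or CT scan in the sum of the product of the biperpendicular diameters of enhancing disease". They do not say which scan the rise is measured from, and neither does the matching definition in protocol 5.2. The only sentence that does is in 9.3.5: "The 12 months MRI or CT scan will be compared to baseline".

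**Early growth.** For growth seen before month 6, section 5.2 says "The first MRI or CT scan showing progression will act as the new baseline". Section 9.3.5 agrees: such growth "will require confirmation 3 months later using the last MRI or CT scan as baseline comparison". Growth first seen at month 6 or later needs no confirmation (5.2).

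**Local scans.** Section 9.3.5 uses locally obtained scans, taken about every 3 to 4 months, to look for progression after month 6. It names no reference scan for them.

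**Unit.** The during-study rule in 5.2 puts its 25% on an "increase in the sum of the biperpendicular diameters of enhancing disease". The SPD definitions in 5.2, the rest of 9.3.5, 12.3.2 and SAP 1.3.2 all use the sum of products.

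**Routes other than size.** The 12-month definition also counts "or new lesions; or substantial worsened T2/FLAIR; or significant clinical neurological decline unexplained by a change in medication or concurrent comorbidities".

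**Use.** One-year PFS is one of two routes to a conclusion of preliminary benefit: at least 11 of 30 alive and progression-free against an expected 27%, or at least 21 of 30 alive against 60% (12.3.2; SAP 1.3.2).

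**The concern.** The trial adopts the immunotherapy criteria so that early enlargement is not taken for progression too soon, and section 5.3 makes it an exploratory endpoint to describe cases "whose imaging was subsequently followed by radiological stabilization or regression". A month-12 comparison that goes back to week 0 could score such a stabilised lesion as progressed after the confirmation step had cleared it.

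The opposite error is also possible. Without a smallest-size reference, a tumour that shrank and is growing again has to climb back past its reference size and a further 25% before the size criterion is met.

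The mismatch of units means that, read literally, the interim and month-12 size rules are different tests carrying the same percentage. All three matter because a margin of one or two patients can decide the 11-of-30 rule. Two careful readers could score the same scans differently.

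**Working it through.** **1. The plan's own cut-offs.** Inputs from 12.3.2: n = 30, null rates 60% (OS) and 27% (PFS), one-sided 0.2. Exact binomial tails:

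- OS: P(X ≥ 20 | 0.60) = 0.292; P(X ≥ 21 | 0.60) = 0.176.
- PFS: P(X ≥ 10 | 0.27) = 0.276; P(X ≥ 11 | 0.27) = 0.161.

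So 21 and 11 are the smallest counts with a tail of 0.2 or less. The plan's figures reproduce.

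**2. Stabilised early growth.** Sizes assumed for illustration: SPD 100 at week 0, then 150 at months 3, 6 and 12.

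- Month 6 against the reset scan: 150/150 − 1 = 0%, so growth is not confirmed.
- Month 12, baseline read as week 0: 150/100 − 1 = +50%, progression.
- Month 12, baseline read as the reset scan: 150/150 − 1 = 0%, not progression.

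The same images give opposite results, depending on one word in 9.3.5.

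**3. Regrowth after shrinkage.** Assumed sizes: SPD 100 at week 0, 40 at month 6, 110 at month 12.

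- Against week 0: 110/100 − 1 = +10%, not progression on size.
- Against the smallest value: 110/40 = 2.75, a rise of 175%.

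In general, with shrinkage s, the growth from the smallest size needed to reach 125% of week 0 is 1.25/(1 − s):

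| Shrinkage | Growth needed, week-0 reference | Growth needed, smallest-SPD reference |
|---|---|---|
| 25% | 1.25/0.75 = 1.67-fold | 1.25-fold |
| 50% | 1.25/0.50 = 2.5-fold | 1.25-fold |
| 60% | 1.25/0.40 = 3.1-fold | 1.25-fold |
| 75% | 1.25/0.25 = 5.0-fold | 1.25-fold |

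The reset reading does not help here: the reset scan is an enlarged one, so its 125% line is higher still.

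**4. Unit.** Take a round lesion with both diameters equal to d, so the sum is 2d and the product d². A 25% rise takes the sum to 2.5d.

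- Both diameters grow: 1.25d × 1.25d = 1.5625d², SPD +56%.
- Only one grows: 1.5d × d = 1.5d², SPD +50%.

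Read literally, the during-study rule needs about twice the SPD rise of the month-12 rule.

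**5. Sensitivity of the 11-of-30 rule.** The numbers of misclassified patients are assumed; each shifts the apparent rate by 1/30.

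| True one-year PFS rate | Net shift | P(X ≥ 11) |
|---|---|---|
| 27% (plan's null) | none | 0.16 |
| 27% | 1 toward progression-free (30.3%) | 0.28 |
| 27% | 2 toward progression-free (33.7%) | 0.43 |
| 40% (assumed) | none | 0.71 |
| 40% | 1 wrongly removed (36.7%) | 0.57 |
| 40% | 2 wrongly removed (33.3%) | 0.42 |

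**The case against.** **Baseline may mean the reset scan.** Section 5.2 calls the first enlarged scan the new baseline, and the sentence in 9.3.5 just before the one at issue uses the word for a later scan too. On that reading the stabilised patient is safe. This stands, so a reader who infers that the plan definitely scores stabilised pseudoprogression as progression goes too far. Week 0 is the plainer reading, because 9.3.5 moves from a qualified comparison scan to plain baseline and elsewhere lists baseline and week 52 as scheduled study scans. The text does not settle it.

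**Regrowth can be caught elsewhere.** A reader might infer that regrowing tumours are counted as progression-free. The documents support only that they are not progression on size. New lesions, T2/FLAIR worsening and neurological decline also count, section 8.4 adds a steroid-need rule, and local scans are read after month 6. This narrows the gap. It leaves local enhancing regrowth in a clinically stable patient, because the local scans have no stated reference.

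**Frequency.** Section 1.1.1 says "An incidence of >20% pseudo-progression has been reported early on post radiochemotherapy", and 20% of 30 is 6. That is not a count of errors: it covers all such cases, including those that regress. The error needs growth seen before month 6 that is unconfirmed and still at least 25% above week 0 at month 12. Patients with no residual lesion after gross total resection are followed for new lesions (9.3.5), so an SPD reference hardly touches them.

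**Pseudoprogression data.** It is tempting to say that the exploratory cases would be overwritten. A month-12 progression label does not erase the imaging dates that section 5.3 needs.

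**The criteria themselves.** The Appendix 1 algorithm is not shown in the text available for this review and may name a reference. It could not be checked.

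**Unit.** SPD is defined just above the during-study rule, and 9.3.5 says SPD is used for comparison, so this may be a slip of wording. That is likely, but the operative sentence still says otherwise.

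**Weight.** Safety is the primary endpoint, the analysis is mainly descriptive, and the OS route is unaffected. This limits the seriousness.

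**Conclusion.** The point holds as a should-fix on a secondary endpoint. Only one sentence names a reference for the month-12 scan. It can be read two ways once section 5.2 has reset the baseline, and no printed section sets a smallest-SPD reference or any reference for the local scans after month 6.

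What follows on both readings is that regrowth after shrinkage is not size-based progression until SPD reaches 125% of the reference. What follows only if baseline means week 0 is that early growth which stabilised at 25% or more above week 0 becomes progression at month 12. The unit mismatch stands apart from both.

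The two reference errors push PFS in opposite directions and the documents give no rate for either, so no net bias can be claimed. Nor can a bias against the 27% benchmark be established, since the documents do not say how the historical trial defined progression. The probabilities above are sensitivities resting on assumed counts and, for the second set, an assumed true rate of 40%. They show that the rule is fragile to one or two classifications; they do not predict that it will fail.

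**What to change.** - In protocol 5.2, 9.3.5 and 12.3.2 and SAP 1.3.2, name one reference for size-based progression on both interim and 12-month scans: the smallest SPD recorded since baseline. After unconfirmed growth before month 6, count from the reset scan onward.
- Keep the week-0 scan as the reference for CR and PR, and say so.
- In the during-study rule of 5.2, put the 25% threshold on the sum of the products of the perpendicular diameters, as elsewhere.
- Check the final wording against the Appendix 1 algorithm.

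This concerns how the endpoint is scored; it does not address treatment decisions at progression.

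The cost is wording in two documents, plus SPD measured on local scans whose copies section 9.3.5 already collects. The downside is more reliance on local scans, which are not acquired under the single-center imaging protocol, for the smallest value.

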### **Performance status**

Performance Status (PS) will be measured using the Karnofsky performance status scale (Appendix 2).

### **9.3.6. Safety assessment**

The NCI CTC-AE version 5.0 will be used to evaluate the clinical safety of the treatment in this study. Patients will be assessed for adverse events at each clinical visit and as necessary throughout the study.

### **Safety Laboratory Assessments**

The following laboratory parameters will be used for patient safety:

#### **Hematology**

- Hemoglobin, platelet count, WBC count, absolute neutrophils and lymphocytes

#### **Coagulation Tests**

- INR, and aPTT

#### **Blood chemistry**

- Including total bilirubin, AST, ALT, LDH, alkaline phosphatase, serum albumin, phosphate, serum creatinine, and electrolytes (sodium, potassium, calcium), glucose, amylase, lipase, TSH, GGT, CK

#### **Urinalysis**

- A urine dipstick test

#### **Pregnancy test**

- Serum  $\beta$ -HCG test indicated in pre-menopausal women who are not surgically sterile and women < 2 years after the onset of menopause

Additional tests may be done at the discretion of the investigator for patient safety.

### **9.3.7. Follow-up**

All patients who discontinue from study treatment will be followed for survival information.

In addition, patients who withdraw from study treatment as a result of progressive disease all further anti-neoplastic treatment, (including surgery and re-irradiation) will be recorded until death or end of the study whichever occurs first.

Survival telephone visits will be performed every 4 weeks until death or the end of the study, whichever occurs first.

For patients who prematurely withdraw from study treatment without documented disease progression:

Disease assessments will be performed until disease progression is observed. All further anti-neoplastic treatment (including surgery and re-irradiation) will be recorded until death or end of the study whichever occurs first. Telephone survival visits will be performed every 4 weeks until death or the end of the study, whichever occurs first.

If the patient withdraws consent, this request must be documented in the source documents, and signed by the investigator. At this time, the patient will be asked if he/she agrees to be followed-up for collection of survival information. This agreement must be documented and signed by the investigator. The study staff may also use a public information source to obtain information about survival status.

